### 3.6 Baseline Characterization

Each analysis sample will be summarized overall and by treatment group for the following characteristics: randomization site; age, sex, race, ethnicity, El Escorial diagnosis, years since ALS symptom onset, delay between symptom onset and ALS diagnosis, site of ALS symptom onset, use of riluzole at baseline, ALSFRS-R total score, SVC, APB muscle strength by HHD on the dominant hand, TMS parameters, TTNCS parameters, cramping frequency, cramping pain, fasciculation intensity, fasciculation interference with daily living, fasciculation interference with sleep, and AUA Symptom Score. The magnitude of differences between treatment groups will be summarized using Fisher's exact tests for nominal variables and two-sample t-tests for approximately continuous variables.

### 3.7 Interim Analysis

An interim analysis for futility was planned after complete follow-up data were available from the 45th ALS participant; however, because the final randomization was scheduled less than three months after this timepoint due to slower than anticipated enrollment, the interim analysis was not conducted, with DSMB approval. The independent DSMB reviewed safety data quarterly and could request specific analyses at any time.

### 3.8 Efficacy Analysis

#### 3.8.1 Primary Analysis of the Primary Efficacy Endpoint

The primary efficacy analysis will be performed on SICI of the APB after log-transformation in the mITT sample of ALS participants and will use a shared-baseline mixed model with fixed effects for visit (6 levels: Screening, Baseline, and Weeks 4, 6, 8, and 12), treatment group (3 levels: placebo and 600 and 900 mg/day ezogabine) x post-baseline visit (4 levels) and random site-specific intercepts and random participant-specific intercepts and slopes with unstructured covariance. The interaction between fixed effects for treatment group and visit will be restricted to post-baseline visits by including a numeric indicator variable (0 pre-treatment, 1 post-treatment) in the interaction. Use of a shared baseline reflects the true state of the population sampled prior to randomization and has the advantage of adjusting for any chance differences at baseline in a manner similar to analysis of covariance (Liang and Zeger, 2000) with potentially greater efficiency with more than one follow-up visit and drop-out. Random participant-specific slopes will be estimated per month from treatment initiation with all pre-treatment observations assigned a value of 0 months from treatment initiation. Data from Final Safety or Early Termination visits will be assigned to the next scheduled post-baseline visit. The following SAS code specifies the model:

```
proc mixed data=xxx method=reml;
  class site id trrnd visit;
  model Value = visit post*trrnd*visit;
  random intercept / subject=site type=vc;
  random intercept month / subject=id(site) type=un;
```

Treatment-dependent differences in the change from pre-treatment to the average of the week 6 and 8 visits on SICI will be estimated by a linear contrast and tested using a two-tailed Wald-test at alpha = 0.027. The following SAS code specifies the linear contrasts used to obtain the two co-primary estimands (with the sort order for treatment group being placebo, 600 mg/day ezogabine, and 900 mg/day ezogabine, and the sort order for visit being chronological):

```
estimate "2|600vsPlb|dAvg 6&8"
  post*ttrrnd*visit 1 1 0 -1 1 0 -1 -1 0 1 1 0 0 0 0 0 0 / cl divisor=2;
estimate "2|900vsPlb|dAvg 6&8"
  post*ttrrnd*visit 1 1 0 -1 -1 0 0 0 0 0 0 -1 1 0 1 1 0 / cl divisor=2;
```

Estimates and their 95% confidence bounds will be back-transformed for reporting as proportional changes. A significant mean reduction in SICI from pre-treatment to the average of weeks 6 and 8 among participants randomized to either 600 or 900 mg/day ezogabine relative to mean changes among participants randomized to placebo would be considered evidence that ezogabine is effective in reducing cortical hyperexcitability.

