## **2.4 Participant Flow and Site Approval**

After providing informed consent, approximately 5 UHC participants will be screened for eligibility at each site, including assessment of neurophysiology by TMS and TTNCS by one or two neurophysiologists. Each UHC participant will have up to 4 additional neurophysiological testing visits over a span of up to 6 weeks.

After completing TMS and TTNCS assessments of the first UHC participant, sites must receive approval from the Coordination Center before continuing enrollment of UHC participants. Approval will be based on review of TMS and TTNCS data by the respective central reading centers. After completing enrollment of approximately 5 UHC participants, sites must receive approval from the Coordination Center before initiating recruitment of ALS participants.

After a site is activated for recruitment of ALS participants and after each ALS patient provides informed consent and is determined eligible, approximately 120 ALS participants will be randomized to receive ezogabine 600 mg/day, ezogabine 900 mg/day, or placebo in a 1:1:1 ratio, stratified by clinical site. The first dose of study drug is administered at the baseline visit. ALS participants are exposed to study drug for 10 weeks, from baseline to a week 10 telephone call. ALS participants complete in-clinic evaluations at weeks 4, 6, 8, and 12 and complete follow-up by telephone at weeks 2, 10, and 14 to assess for TEAEs and update concomitant medication logs. Participants who discontinue study drug should remain on study following the normal schedule of assessments. Patients withdrawing consent are asked to delay withdrawing consent until after they return for a Final Safety Visit approximately 2 weeks after their last dose of study drug and after they complete a final telephone call 4 weeks after their last dose of study drug.

Detailed descriptions of study procedures and timing are specified in the clinical protocol.

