## 3.4 Determination of Sample Size

Caramia et al. (2000) report mean (SD) paired pulse SICI at 3 ms among 16 ALS patients of 125.7 (25.7) percent of MEP control size. Stefan et al. (2001) report paired pulse SICI at 3 ms among 13 ALS patients of 96.9 (35.9) percent of MEP control size. Assuming a mean (SD) equal to 100 (30) percent of MEP and using a two-sided alpha of 0.027 based on Dunnett's correction for comparing two treatments to placebo, 40 patients in each group and up to 25% loss to follow-up would give 80% power to detect a 25% difference between placebo and each active treatment based on a simple two-sample t-test. This accommodates the loss of power due to early stopping for futility and is conservative relative to our proposed shared-baseline mixed model analysis. For reference, Caramia et al. (2000) report an effect of three-week exposure to gabapentin equal to an 80% reduction of the paired pulse amplitude in untreated patients, and Stefan et al. (2001) report an effect of 5 or more day exposure to riluzole equal to a 35% reduction of the conditioned stimulus amplitude.

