### 3.8.5 Multiplicity Adjustments

The effect of each dose of ezogabine on the primary efficacy outcome in the mITT sample will be tested at two-tailed  $p < 0.027$  following Dunnett's correction for comparing two active treatments to placebo. If this primary analysis identifies a significant benefit from ezogabine treatment, then testing the key secondary efficacy outcome at  $p < 0.027$  maintains an overall type I error rate at 5% under a closed testing sequential analysis. If significance of the key secondary outcome alone is accepted as evidence of a therapeutic benefit from ezogabine when the primary analysis is not significant, then the overall type I error rate will be limited to 10% or less (depending on the correlation between the primary and key secondary outcomes). Results from analysis of non-key secondary efficacy endpoints, exploratory efficacy endpoints, and subgroup analyses will report nominal, comparison-wise p-values, recognizing that the totality of results will be evaluated in judging the potential efficacy of ezogabine.

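### The two primary SICI contrasts use a Wald test with no small-sample correction, so the overall type I error is slightly above the stated 5% (about 5.2 to 5.9% at 120 participants)

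*SAP*

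**What the plan says.** SAP 3.8.1 fits log SICI by REML ("proc mixed data=xxx method=reml"). The fixed effects are given by "model Value = visit post*trrnd*visit". There is a random site intercept, and the participant effects are "random intercept month / subject=id(site) type=un". Each dose is compared with placebo by a linear contrast on the Week 6 and Week 8 average, "tested using a two-tailed Wald-test at alpha = 0.027". The MODEL statement carries no `ddfm=` option, and neither does the one for the random-slopes model in SAP 3.8.2.

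SAP 3.8.5 and Protocol 13.6 explain the level: 0.027 is used "following Dunnett's correction for comparing two active treatments to placebo", and testing the key secondary endpoint at the same level after a significant primary result "maintains an overall type I error rate at 5% under a closed testing sequential analysis".

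On size, SAP 2.4 has "approximately 120 ALS participants will be randomized to receive ezogabine 600 mg/day, ezogabine 900 mg/day, or placebo in a 1:1:1 ratio", and SAP 3.4 states that "40 patients in each group and up to 25% loss to follow-up would give 80% power to detect a 25% difference". SAP 3.1.1 permits either SAS or R.

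**The concern.** A Wald test treats the estimated standard error as if it were known. Here the standard error depends on four participant-level and residual variance parameters and a site variance. They are estimated from about 30 evaluable people per arm, most of whom have TMS at only four visits (SAP 2.8, note 17). If the reference distribution is too narrow, 0.027 per dose no longer delivers the 5% that the SAP claims.

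The text is also ambiguous. It does not say whether the reference is normal or t, nor on how many degrees of freedom. PROC MIXED will choose a default, and an R routine need not choose the same one. Two careful analysts could therefore report different p-values near 0.027 for the co-primary contrasts. The key secondary endpoint (RMT) and the other continuous endpoints inherit the same test through SAP 3.8.3.

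**Working it through.** **1. The plan's own figure.** With two active arms, one shared placebo and equal allocation, the two test statistics have correlation 0.5. Two-sided 0.027 corresponds to z = 2.2115. Integrating the bivariate normal, P(|Z1| > 2.2115 or |Z2| > 2.2115) = 5.01%. The SAP's level is therefore reproduced, as the known-variance Dunnett level.

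**2. What the printed code does by default.** No random effect syntactically contains `post*trrnd*visit`. The containment default therefore falls back on residual degrees of freedom: observations minus the rank of the fixed plus random effects together. At 120 participants with 25% lost before Week 6:
- observations: 90 × 4 + 30 × 2 = 420
- participant intercepts and slopes: 120 + 90 = 210
- remainder: 420 − 210 = 210, less a few fixed-effect columns, or about 204 in the simulated fits

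The Satterthwaite value for the dose contrasts in the same setting has a median of about 90.

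**3. Effect on the critical value at two-sided 0.027.**

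| Reference | Critical value |
|---|---|
| normal (literal Wald z) | 2.212 |
| t, 204 df (approximate SAS default) | 2.228 |
| t, 90 df (Satterthwaite) | 2.248 |

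**4. Idealised check.** Suppose both contrasts share one variance estimate on 90 df. The overall error is then 5.44% with the z limit, 5.24% with the 204-df limit and 4.99% with the 90-df limit. To reach 6.0% with the z limit, the variance would have to rest on about 40 df.

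**5. Simulation of the SAP model under no effect.** From the documents: 120 participants, 1:1:1, 12 sites, TMS at Screening, Baseline, Weeks 6 and 8, and 25% without Week 6 or 8 data. Assumed: three sets of (intercept, monthly slope, residual, site) variances, namely (1, 0.1, 1, 0.1), (1, 0.3, 0.5, 0.1) and (0.5, 0.05, 1, 0.05), with zero intercept-slope correlation and data missing completely at random. Each main scenario had 12,000 runs, with the known-variance test as control variate (Monte Carlo SE about 0.14 points). An error is rejection of either contrast.

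| Setting, N = 120 | z | residual df |
|---|---|---|
| three variance sets | 5.5 to 5.9% | 5.2 to 5.6% |
| same, 15% of assessments also lost to quality flags (rate assumed) | 5.5 to 5.7% | 5.2 to 5.5% |
| SDs 0.4, 0.14, 0.3 (intercept, slope, residual), no site effect, 25% loss plus 5% sporadic | 5.6% | 5.4% |
| same SDs, 10% loss | 5.8% | 5.7% |

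The last two rows are separate runs of 9,500 and 8,500 trials (SE about 0.15). Smaller runs on those SDs without a control variate gave 6.2% (z) and 5.8 to 6.0% (residual df). Their SE was 0.3 to 0.4 points, so they are less reliable.

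**6. After a correction, N = 120.** A t reference on Satterthwaite df gave about 5.4% (SE 0.2 to 0.3), against 5.7 to 5.9% for z in the same runs. Kenward-Roger, in the smaller runs without a control variate, gave 5.3 to 5.4% (SE 0.3 to 0.4), against 6.2% for z. Both remove part or all of the excess, and this precision cannot separate them.

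**7. Fewer participants (illustration only).** At 90 in total the same method gives 5.6 to 6.0% (z) and 5.4 to 5.7% (residual df). At 66 it gives 5.5 to 6.5% and 5.3 to 6.3%. Neither size comes from the documents.

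**The case against.** The strongest reply is that the excess is too small to matter. This is a phase 2 pharmacodynamic study. SAP 3.8.5 itself contemplates an overall error of up to 10% if the key secondary endpoint alone is accepted as evidence. An excess below one point changes a conclusion only for p-values in a narrow band around 0.027. That argument stands as to severity. It does not remove the point, because the same section claims 5% for the sequential procedure and the named test does not quite give it.

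A second reply is that the larger z figures do not describe the printed code, since PROC MIXED would use a t reference on residual df. That is fair if SAS is used as printed. But the text says Wald and R is allowed, so the SAP leaves the choice open.

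A reader might infer something stronger: that the error is 6% or more at the planned size, or above 7% because enrolment was slow. The documents do not support this. At 120 participants, 6% lies just above the range of the more precise simulations. SAP 3.7 reports slow enrolment but gives no final number. A total of 45 also conflicts with SAP 3.7, which places the final randomisation after complete follow-up of the 45th participant. Nor do the documents give variance components for log SICI, so no single figure can be claimed.

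**Conclusion.** The point holds as a minor one. The SAP names a Wald test with plug-in standard errors, states no denominator degrees of freedom, and sets the per-dose level with no slack. At about 120 participants the overall type I error for the two SICI contrasts is about 5.2 to 5.7% on the SAS default and 5.5 to 5.9% on a normal reference, an excess of roughly 0.2 to 0.9 points. Direction and mechanism are secure. Confidence in the size is medium, because it rests on assumed variance components, on the planning ceiling of 25% loss in most scenarios and on data missing completely at random. The excess rises modestly as numbers fall, which also bears on the smaller low-RMT sample in SAP 3.5. Treatment estimates are not affected; only p-values and interval widths are.

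**What to change.** Before unblinding, add `ddfm=kr` to the MODEL statements in SAP 3.8.1 and 3.8.2. In 3.8.1, replace the Wald test by: *two-tailed t-test with Kenward-Roger standard error and degrees of freedom at alpha = 0.027*. State that the same method applies if the model is fitted in R, and that it carries over to RMT and the other continuous endpoints under 3.8.3. Keep 0.027. Satterthwaite degrees of freedom would be an acceptable second choice at this size, but they leave the standard error unadjusted.

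The cost is one code option and one or two sentences. Design, data and estimand stay as they are. P-values and confidence intervals become slightly less favourable: on 90 degrees of freedom, a statistic exactly at the z limit of 2.2115 has p = 0.0295 rather than 0.027.

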### 13.3 Primary Analysis

We will test the effect of ezogabine on SICI using the mITT sample of ALS subjects in a shared-baseline mixed model with fixed effects for visit (6 levels: Screening, Baseline, and Weeks 4, 6, 8, and 12), treatment group (3 levels: placebo and 600 and 900 mg/day ezogabine) x post-baseline visit (4 levels) and random site-specific intercepts and random participant-specific intercepts and slopes with unstructured covariance. The use of a shared-baseline reflects the homogeneity of the trial cohort prior to randomization and the combination with participant-specific random effects induces an adjustment for any chance baseline differences similar to ANCOVA (Liu et al, 2009). We will use linear contrasts to test for dose-dependent differences in change from baseline to the average SICI over the stable dose period from weeks 6 through 8. A significant reduction of SICI (i.e., higher MEP amplitude) of either dose relative to placebo would be accepted as evidence of benefit from ezogabine treatment.

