### 3.8.2 Secondary Analyses of the Primary Efficacy Endpoint

Several secondary analyses will be investigated to assess sensitivity of our estimates of treatment effect to alternative modeling assumptions.

- Active vs. placebo: A secondary estimand of the efficacy of ezogabine will compare both 600 mg/day and 900 mg/day treatment arms vs. placebo, tested at alpha = 0.05. The following SAS code specifies the linear contrast for this comparison:

```
estimate "2|ActvsPlb|dAvg 6&8"
  post*ttrrnd*visit 2 2 0 -2 -2 0 -1 -1 0 1 1 0 -1 -1 0 1 1 0 / cl divisor=4;
```

- Random-slopes model: The visit-specific fixed effects will be replaced with a continuous predictor of month since treatment initiation. Data from Final Safety and Early Termination visits will be placed at their observed follow-up time. Only assessments completed through Week 10, the end of planned study drug exposure, will be included. The following SAS code specifies the model and the linear contrasts used to estimate treatment-dependent differences in rate of change per month:

```
proc mixed data=xxx method=reml;
  where visit in ("Screening","Baseline","Week 04","Week 06","Week 08","Week 10");
  class site id ttrrnd;
  model Value = month ttrrnd*month;
  random intercept / subject=site type=vc;
  random intercept month / subject=id(site) type=un;
estimate "2|600vsPbl|Slope/mn" intercept 0 month 0 ttrrnd*month -1 1 0 / cl;
estimate "2|900vsPbl|Slope/mn" intercept 0 month 0 ttrrnd*month -1 0 1 / cl;
estimate "2|ActvsPbl|Slope/mn" intercept 0 month 0 ttrrnd*month -2 1 1 / cl divisor=2;
```

- Shared-baseline mixed model with pMI for missing data: The shared-baseline mixed model with fixed effects for visits described above for the primary analysis will be applied to datasets generated by placebo multiple imputation (Ayele et al. 2014). Fifty imputed datasets will be generated for a given endpoint.
- PP sample: The primary efficacy model and the secondary random-slopes model and active vs. placebo estimand will be applied to the PP sample.
- loRMT sample: The primary efficacy model and the secondary random-slopes model and active vs. placebo estimand will be applied to the loRMT sample.

- AllQual sample: The primary efficacy model and the secondary random-slopes model and active vs. placebo estimand will be applied to the AllQual sample.

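### The three shared-baseline ESTIMATE statements, including both co-primary contrasts, weight Screening and Baseline cells that the model makes identically zero, so they are not estimable as written

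*SAP*

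**What the plan says.** Protocol 13.3 defines the interaction as "treatment group (3 levels: placebo and 600 and 900 mg/day ezogabine) x post-baseline visit (4 levels"), which is 3 × 4 = 12 cells. SAP 3.8.1 repeats this and implements it by "including a numeric indicator variable (0 pre-treatment, 1 post-treatment) in the interaction". The model line is "model Value = visit post*trrnd*visit". The indicator `post` is not among the CLASS variables, so it is numeric.

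The SAP gives the code the status of a specification: "The following SAS code specifies the linear contrasts used to obtain the two co-primary estimands". Coefficients run placebo, 600 mg, 900 mg, with visits in chronological order within each arm. The statements are:

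- 600 mg vs placebo (3.8.1): "post*ttrrnd*visit 1 1 0 -1 1 0 -1 -1 0 1 1 0 0 0 0 0 0 / cl divisor=2"
- 900 mg vs placebo (3.8.1): "post*ttrrnd*visit 1 1 0 -1 -1 0 0 0 0 0 0 -1 1 0 1 1 0 / cl divisor=2"
- both doses vs placebo (3.8.2): "post*ttrrnd*visit 2 2 0 -2 -2 0 -1 -1 0 1 1 0 -1 -1 0 1 1 0 / cl divisor=4"

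The two dose contrasts are the co-primary tests, at two-sided alpha 0.027. Neither section puts coefficients on the visit main effect or relaxes the estimability check.

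**The concern.** The contrasts are written as a difference of changes, with explicit pre-treatment terms in each arm. That form belongs to an unrestricted treatment-by-visit model. In the model the SAP specifies, the pre-treatment interaction cells carry no information, and a contrast that weights them is not a function of the fitted means.

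The consequence is procedural. The SAP is authoritative over the protocol on matters of analysis, and the primary model is reused for the placebo-imputation analysis, the per-protocol, low-RMT and all-quality samples, the key secondary endpoint (RMT), and the other continuous efficacy endpoints. If the code were followed exactly, the pre-specified co-primary tests should give no valid result, and someone would have to rewrite them when the data are in hand.

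**Working it through.** **Design matrix.** The fixed effects give 1 intercept + 6 visit columns + 3 × 6 = 18 interaction columns, 25 in all. With `post` = 0 at Screening and Baseline, 3 arms × 2 visits = 6 interaction columns are all zero. The rank is 2 pre-treatment means + 3 × 4 post-baseline means = 14; the numerical rank agrees.

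**Criterion.** A contrast K is estimable only if K = K(X′X)⁻(X′X), that is, if K is a linear combination of rows of X. Every row of X is 0 in those six columns, so any K with a non-zero weight there fails. Because these lines put no weight on the visit main effect, K must also sum to zero across arms at each post-baseline visit.

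**Restoring the dose lines.** In the text copy each dose line has 17 values. Adding one 0 and one minus sign to each gives a full difference-of-changes contrast, and the two restored lines add up to the printed active line in all 18 cells:

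- 600: `1 1 0 -1 -1 0 | -1 -1 0 1 1 0 | 0 0 0 0 0 0`
- 900: `1 1 0 -1 -1 0 | 0 0 0 0 0 0 | -1 -1 0 1 1 0`

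**Results.** The gap is the largest absolute element of K − K(X′X)⁻(X′X), before the divisor. The 17-value lines were padded with a trailing 0, which is an assumption.

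| Statement | Non-zero weights on zero columns | Gap | Gap with pre-treatment weights set to 0 |
|---|---|---|---|
| Active vs placebo, as printed | 6 of 12 | 2.0 | 0 |
| 600 vs placebo, restored | 4 of 8 | 1.0 | 0 |
| 900 vs placebo, restored | 4 of 8 | 1.0 | 0 |
| 600 vs placebo, as supplied | 4 of 8 | 1.0 | 0.52 |
| 900 vs placebo, as supplied | 3 of 8 | 1.0 | 0.28 |

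The three random-slopes ESTIMATE statements in SAP 3.8.2 pass the same test (gap below 1e-15), so the check does not reject everything. The assumed numbers of patients (40 per arm, 15 per arm at Weeks 4 and 12) do not affect the outcome: estimability depends only on which arm-by-visit cells hold data.

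**Why zero is the right weight.** Write the mean as μ + visit(v) before treatment, shared by all arms, and μ + visit(v) + τ(arm, v) afterwards. The difference, dose minus placebo, in change from the pre-treatment mean to the average of Weeks 6 and 8 is then

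½[τ(dose,6) + τ(dose,8) − τ(placebo,6) − τ(placebo,8)].

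The pre-treatment and visit terms cancel. In the restored lines and the active line the pre-treatment weights also sum to 0 across arms (1 − 1 for each dose line; 2 − 1 − 1 for the active line), so deleting them leaves the estimand unchanged. In one simulated data set with the zero-column parameters set to 0, restored and corrected contrasts agreed: 600 vs placebo −0.187 (SE 0.078) and active vs placebo −0.211 (SE 0.067), both ways.

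**Test of the replacement lines on dummy data.** The assumed ratios to placebo at Weeks 6 and 8 were 0.85 and 0.75 (600) and 0.80 and 0.65 (900). The true log contrasts are (ln 0.85 + ln 0.75)/2 = −0.2251, (ln 0.80 + ln 0.65)/2 = −0.3270, and their mean, −0.2760, for active. Noise-free data return these values. Over 4,000 simulated trials (generalised least squares with known covariance) the means were −0.2236, −0.3279 and −0.2757, with Monte Carlo standard errors 0.0014, 0.0014 and 0.0012.

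**Points to check against the source PDF.** As supplied, each dose line sums to +2, not 0. The 600 line has +1 at placebo Week 8 where −1 is expected. The 900 line is shifted: it weights 600 mg Week 12 and 900 mg Week 4 and omits 900 mg Week 8. The treatment variable is `trrnd` in CLASS and MODEL of 3.8.1 but `ttrrnd` in its ESTIMATE lines; 3.8.2 uses the second spelling throughout, as in "class site id ttrrnd".

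**The case against.** The strongest reply is that nothing inferential turns on this. The prose states the estimand, model, sort order, test and alpha, and only one repair fits. A dry run would expose the fault, and the estimate and its standard error are the same once the empty cells are dropped. That is correct, and it is why the point is minor. It does not make the specified code correct.

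A second reply is that the dose lines look damaged by text extraction, so the only intact evidence is the active-versus-placebo line, a secondary comparison at alpha 0.05. The coefficient counts, signs and variable spelling may well be reading damage; the pattern (one 0 and one minus sign lost from each line) suggests it, and only the source PDF can settle it. The main point does not depend on them. The intact line fails solely through its pre-treatment weights, and both dose lines fail as supplied and as restored.

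Third, SAS was not run, and SAP 3.1.1 also allows R, where the statements would have to be rewritten anyway. A non-estimable result is therefore what the algebra leads one to expect; it has not been observed.

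**Conclusion.** The concern holds, as a minor one. Three of the SAP's six ESTIMATE statements, all three for the shared-baseline model, are not estimable under the model they accompany; the three random-slopes statements are sound. The conclusion rests on `post` being numeric and coded as the SAP describes, on the stated sort order, and on the estimability check being left in force. For the two co-primary lines it holds for both the supplied and the restored text. The expected outcome is a visible failure, not a silently wrong answer. What remains is that the co-primary contrasts do not stand correct in the pre-specified plan.

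**What to change.** Replace the three coefficient lists, in the order placebo, 600, 900:

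- 600 vs placebo: `0 0 0 -1 -1 0 0 0 0 1 1 0 0 0 0 0 0 0 / cl divisor=2`
- 900 vs placebo: `0 0 0 -1 -1 0 0 0 0 0 0 0 0 0 0 1 1 0 / cl divisor=2`
- active vs placebo: `0 0 0 -2 -2 0 0 0 0 1 1 0 0 0 0 1 1 0 / cl divisor=4`

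These lines also settle the coefficient counts and signs whatever the source PDF shows. Deleting the pre-treatment weights alone would not repair the two dose lines as supplied. Use one treatment variable name throughout, and run the code on dummy-treatment data before the analysis. The cost is three code lines and one variable name; the estimand, alpha, model and sample size do not change.
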